10.4.2 Analysis of Key Study Endpoints

10.4.2.1 Primary Endpoint Analyses

Adverse events will be coded using the latest version of Medical Dictionary for Regulatory Activities (MedDRA). Subject incidences of adverse events, serious adverse

events, and adverse events leading to withdrawal will be tabulated by system organ class and preferred term for each treatment group.

Subgroup analyses on the primary endpoint will be conducted by parent study.

10.4.2.2 Secondary Endpoint Analyses

Point estimates of treatment group means and their 95% confidence intervals will be calculated using a mixed effects model containing the stratification factors, treatment group, visit, and treatment group by visit. Differences in group means for the secondary and exploratory endpoints will be estimated between the AMG 145 + SOC group and the SOC-alone group.

Subgroup analyses for secondary endpoints may be conducted on baseline covariates specified in [Section 10.1.6](#).

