10.1.6 Baseline Covariates

The stratification factors are the parent study and the randomized treatment dose frequency in the parent study (Q2W or QM).

Baseline covariates for subgroup analyses include, but are not limited to:

- Age
- Sex
- Race
- LDL-C
- Family history of premature coronary heart disease

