IVRS	Interactive voice response system
LDL-C	Low density lipoprotein cholesterol
LFT	Liver Function Test
Lp(a)	Lipoprotein(a)
MedDRA	Medical dictionary for regulatory activities
OLE	Open label extension
QM	Every month
Q2W	Every 2 weeks
SOC	Standard of care
SAP	Statistical analysis plan
TIA	Transient ischemic attack
ULN	Upper limit of normal
VLDL-C	Very low density lipoprotein cholesterol

1. Introduction

The purpose of this interim SAP is to pre-specify interim analyses to support regulatory filings. The analysis strategy is consistent with the protocol specified analysis. Analyses will be performed based on datasets of an ongoing study 20120138, entitled A Multicenter, Controlled, Open-label (OLE) Study to Assess the Long-term Safety and Efficacy of AMG 145 (latest amendment 2 is 30 APR 2013).

2. Objectives

The objective for this analysis is to summarize the safety and lipid data collected up to a cutoff date reported in the table outputs for subjects rolled over from parent studies into the extension study 20120138. All data prior to the data cut date will be collected, checked and queried in the similar fashion as the final database lock.

3. Endpoints

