3.2 Secondary Endpoints

- Percent change from baseline in LDL-C at each visit with planned lipid measurements
- Change from baseline in LDL-C at each visit with planned lipid measurements
- Percent change from parent study EOS in LDL-C at each visit with planned lipid measurements
- Change from parent study EOS in LDL-C at each visit with planned lipid measurements

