Sex

For subjects that enroll in an extension study, the subject's sex is the sex recorded on the extension study eCRF. For other subjects, the subject's sex is the sex recorded on the parent study eCRF.

Race

For subjects that enroll in an extension study, the subject's race is the race recorded on the extension study eCRF. For other subjects, the subject's race is the race recorded on the parent study eCRF.

Country and Region

For subjects that enroll in an extension study, the subject's country and region are those recorded in the extension study. For other subjects, the subject's country and region are those recorded in the parent study.

Baseline Metabolic Syndrome

For each subject without type 2 diabetes mellitus, metabolic syndrome is identified by the presence of 3 or more of the components listed below (modified AHA/NHLBI criteria). Subjects with type 2 diabetes cannot be categorized as having metabolic syndrome.

Risk Factor	Defining Level
Elevated waist circumference:	
Non-Asian:	
Men	≥ 102 cm
Women	≥ 88 cm
Asian:	
Men	≥ 90 cm
Women	≥ 80 cm
Triglycerides	≥ 150 mg/dL
HDL cholesterol	
Men	< 40 mg/dL
Women	< 50 mg/dL
Blood pressure	SBP ≥ 130 mmHg or DBP ≥ 85 mmHg OR Hypertension checked 'yes' on CV Medical History eCRF
Fasting glucose	≥ 100 mg/dL

4-Level Treatment Group

All tables in this interim analysis will be summarized by randomized group (AMG 145+SOC vs. SOC alone). Since subjects received either AMG 145 or control treatment in parent study, the tables will be further categorized using the following 4 levels (parent study treatment group/current study treatment group): "AMG 145/AMG 145 + SOC"; "AMG 145/SOC Only"; "Control/AMG 145 + SOC", and "Control/SOC Only".

6. Analysis Subsets

Interim SOC-Controlled period Analysis Set

The Interim SOC-**C**ontrolled period **A**nalysis **S**et (ICOAS) will include all subjects randomized in this study who have at least 12 weeks of potential follow-up (eg. subjects for whom Data Cutoff Date - Study Date for Study Day 1 + 1 > 91 days); the restriction on potential follow-up is to prevent operational bias that may occur by the increased frequency of visits during the first 12 weeks of the study. Subjects will be analyzed according to the treatment group to which they were randomized during the SOC-Controlled period. All data from the SOC-Controlled period will be summarized, regardless of possible IP discontinuation.

Interim All-IP period Analysis Set

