7.6 Distributional Characteristics

There are no distributional requirements for the planned analyses. Therefore no assessment will be made.

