8.4.2 Analyses of Secondary Endpoints

The secondary endpoints for percent change and absolute change from baseline will be summarized for each scheduled visit. These secondary endpoint analyses will be repeated using change from parent EOS and percent change from parent EOS and summarized with descriptive statistics at each scheduled visit. All analyses will be performed separately for each of the ICOAS and IAAS analysis sets.

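### SAP Appendix A has no randomized-period window for Week 48 lipids, so Week 48 LDL-C is summarised only in a set defined by dosing after randomization, and some Week 48 samples are handled as Week 24

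*Protocol*

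**What the plan says.** **Protocol (Amendment 6).** Section 10.1.2 makes change and percent change in LDL-C at Weeks 48 and 104 the secondary endpoints. Section 10.4.2.2 estimates group means with 95% intervals "using a mixed effects model containing the stratification factors, treatment group, visit, and treatment group by visit" and also calls for between-group differences. Section 10.1.6 names parent study and parent dosing frequency as the stratification factors and lists baseline LDL-C only for subgroup analyses. Section 10.1.5 assigns randomized-period analyses to all randomized subjects and allows later-period analyses to be limited to those receiving investigational product (IP).

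**Interim SAP.** Section 1 states: "The purpose of this interim SAP is to pre-specify interim analyses to support regulatory filings". It adds "The analysis strategy is consistent with the protocol specified analysis", with reference to Amendment 2. Section 3.2 lists "Percent change from baseline in LDL-C at each visit with planned lipid measurements". For the analysis, 8.4.2 says only "The secondary endpoints for percent change and absolute change from baseline will be summarized for each scheduled visit", separately for the two analysis sets. Section 8.1 lists summary statistics without a confidence interval, and 7.6 says "There are no distributional requirements for the planned analyses".

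**Periods, sets and windows in the SAP.**
- Section 5.1: the SOC-Controlled period ends the day before the Week 48 dose. If no dose is given at Week 48, it ends at the earliest of Day 343, end of study or data cutoff. The All-IP period starts the next day.
- Section 6: the ICOAS covers randomized subjects with at least 12 weeks of potential follow-up, and "All data from the SOC-Controlled period will be summarized, regardless of possible IP discontinuation". The IAAS covers randomized subjects dosed with IP and on study in the All-IP period.
- Appendix A, both lab tables: the Week 24 lipid window runs from after Day 126 to the end of the SOC-Controlled period. The Week 48 window starts with the All-IP period and ends at Day 420, or at Day 378 for SOC subjects who were controls in the parent study. If a window holds several records, the one nearest Day 7 x week + 1 is used.

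**The concern.** Week 48 is the last lipid visit at which the arms can be compared as randomized, because SOC-alone subjects then start AMG 145. Under the SAP's rules no lipid value can carry a Week 48 label while it belongs to the randomized period. The label exists only in a period whose analysis set depends on dosing after randomization. Other samples taken at the Week 48 visit are treated as Week 24 candidates.

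Two things are at stake. First, Week 48 values in subjects who are off AMG 145, or who never start it, can drop out of every visit summary, although SAP section 6 says stopping IP does not remove data. Second, a Week 48 contrast read from the by-arm tables would not compare the groups as randomized. These tables are meant to support regulatory filings.

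The missing difference and interval in SAP 8.4.2, and the missing baseline term in protocol 10.4.2.2, are smaller matters.

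**Working it through.** **1. The plan's own precision figure.** None is given for LDL-C. The only one is the interval for a 5% adverse event incidence in protocol 10.2. With 4428 subjects allocated 2:1, the arms are 1476 and 2952. Exact 95% intervals are 74/1476: (3.96%, 6.25%) and 148/2952: (4.25%, 5.86%). These round to the stated (4.0%, 6.3%) and (4.3%, 5.9%), so these arm sizes are used below.

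**2. Tracing a Week 48 sample.** Target days are 7 x 24 + 1 = 169 and 7 x 48 + 1 = 337. The protocol's 7-day allowance gives visit days 330-344.

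| Case | Period of the sample | Lipid window |
|---|---|---|
| Dosed the same day, after the draw | First day of All-IP | Week 48 |
| Dosed on a later day | SOC-Controlled | Week 24 |
| Not dosed at Week 48, sample on Days 330-343 | SOC-Controlled | Week 24 |
| Not dosed at Week 48, still on study, sample on Day 344 | All-IP | Week 48, if in the IAAS |

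The second row matters for adherent subjects. Protocol 7.1.1.14 and the schedule footnotes place observed Week 48 dosing in SOC-alone subjects; for AMG 145 + SOC subjects the visit provides dispensing for home use. A home dose on Day 339 after a draw on Day 337 puts that draw in the Week 24 window. The third row covers 14 of the 15 visit days.

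**3. What happens in the Week 24 window.** A sample on Day s (330 or later) is s - 169 days from target, at least 161. An earlier record on Day d, with d from 127 to s - 1, is at most the larger of 42 and s - 170 days away. Both are less than s - 169. The Week 48 sample therefore loses to any earlier record in the window. It is used only if there is none, and is then reported as Week 24.

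**4. Who is left out of the Week 48 row.** SOC-alone subjects who never start AMG 145 are outside the IAAS. AMG 145 + SOC subjects who stopped are outside it if the All-IP condition applies to dosing as well as to being on study. If it applies only to being on study, they belong to the set, but step 2 still sends their Day 330-343 samples to Week 24.

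**5. Illustrative size of the exclusion (inputs assumed).** Let a share q of sampled AMG 145 + SOC subjects be left out with 0% change, and let the others fall by R points. The all-sampled mean is -(1 - q)R and the reported mean is -R, so the reduction is overstated by qR. With R = 50 to 60:
- q = 1%: 0.5 to 0.6 points
- q = 5%: 2.5 to 3.0 points
- q = 10%: 5.0 to 6.0 points

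If those left out sit anywhere from 0 to -20% and the others at -55%, q = 5% gives 0.05 x 35 = 1.75 to 0.05 x 55 = 2.75 points.

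**6. Size of the baseline omission (SD and correlation assumed).** Half-width = 1.96 x SD x sqrt(1/1476 + 1/2952) = 0.0625 x SD. This is 1.25, 1.87 and 2.50 points for SD 20, 30 and 40. With a common slope and correlation r, adjustment multiplies it by sqrt(1 - r^2). At SD 30 this gives 1.79 (r = 0.3) or 1.62 (r = 0.5), a gain of 0.09 or 0.25 points.

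The gain is not guaranteed under 2:1 allocation. With AMG 145 share p = 2/3 and baseline variance V, a common slope lowers N x variance by V/(p(1-p)) x pooled slope x SOC slope. Take slopes of +0.20 (AMG 145) and -0.15 (SOC), baseline SD 40 and residual SDs 22 and 20:
- Unadjusted N x variance: (484 + 64)/(2/3) + (400 + 36)/(1/3) = 2130.
- Pooled slope: (2/3)(0.20) + (1/3)(-0.15) = 0.0833. The change is 7200 x 0.0833 x (-0.15) = -90, so the variance is 4.2% worse.
- With a treatment-by-baseline term, the effective slope is (1/3)(0.20) + (2/3)(-0.15) = -0.0333. The gain is 7200 x 0.0333^2 = 8, or 0.4% better.

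**The case against.** **The analysis is descriptive and may not be the Week 48 interim.** The ICOAS needs only 12 weeks of potential follow-up, whereas protocol 10.3 describes an interim after sets of parent studies complete Week 48. The documents do not show that these are the same analysis, and the SAP plans no Week 48 contrast. That stands, and it limits the harm to what the tables display and what readers derive from them. The SAP nevertheless has a Week 48 lipid row and promises a summary at every planned lipid visit.

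**The documents are not a matched pair.** The SAP cites Amendment 2 and the supplied protocol is Amendment 6. Appendix A has lipid windows at Weeks 72 and 96, where Amendment 6 draws no lipids; it draws them at Week 84. A reader might infer that the SAP's statement of consistency with the protocol is false. This cannot be shown without the Amendment 2 text. The visit allowance, pre-dose draw and dispensing details used above are also Amendment 6 text. The period, set and window rules are the SAP's own, as is their conflict with its section 6.

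**The IAAS wording has two readings.** SAP 5.3 sets All-IP exposure to zero when the formula is negative, which suggests that subjects who stopped earlier may belong to the set. This is a fair point, so the set wording alone does not establish that they are excluded. Never-dosed SOC-alone subjects are excluded on both readings.

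**A baseline covariate is optional.** The outcome is already a change from baseline, and a common slope can lose precision. This is correct, and it is why the covariate is only a secondary point.

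**Conclusion.** The window defect holds. The ICOAS has lipid rows only for Weeks 0, 12 and 24. A Week 48 label exists only in the All-IP period. Week 48 samples taken before the dose date, or on Days 330-343 without a Week 48 dose, become Week 24 records or disappear. This conflicts with the SAP's statement that SOC-Controlled data are summarised whatever happens to IP.

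The number of subjects affected is unknown. The 2.5-3.0 points at 5% excluded is an illustration that rests on an assumed rate, an assumed full return to baseline and the exclusion itself. It would equal or exceed the assumed half-widths of 1.25 to 2.50 points, but at 1% excluded the shift is only 0.5-0.6.

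Stronger readings are not supported:
- Week 48 samples do not all fall on the first All-IP day. That needs same-day dosing.
- Leaving baseline LDL-C out of the model does not bias the randomized comparison if data are complete or missing at random given the model. The cost is interval width, about 0.1 to 0.25 points in the example.
- The missing difference and interval in SAP 8.4.2 do not show that they will never be reported. No final SAP is supplied, and protocol 10.4.2.2 still plans model-based means with intervals and between-group differences.

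**What to change.** **SAP Appendix A, both lab tables.** Give lipids their own column so that safety-laboratory windows stay as they are. Set Week 24 to (126, 252] and add a randomized-period Week 48 window starting after Day 252 with one upper bound for both arms. Day 378, already used for one SOC group, would serve. Day 252 = 7 x 36 and Day 378 = 7 x 54, so all Week 24 visit days (162-176) and all Week 48 visit days (330-344) fall where they belong. Count SOC-alone samples only up to and including the pre-dose sample on the first AMG 145 dose date. Apply the window to all ICOAS subjects whatever their dosing.

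**SAP 6.** State whether the All-IP condition applies to dosing, to being on study, or to both.

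**SAP 8.4.2.** Report the AMG 145 + SOC minus SOC-alone LDL-C difference with 95% CI at Weeks 12, 24 and 48, in ICOAS subjects whose potential follow-up at the cutoff covers the visit. Keep the All-IP Week 48 table as a separate, labelled display.

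**Protocol 10.4.2.2.** Add baseline LDL-C and baseline by visit. A treatment-by-baseline term, with baseline centred, is an option because a common slope may gain little or lose slightly under 2:1 allocation.

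**Cost.** One extra table, a split column in two window tables, a few model terms, and a footnote that the lipid window differs from the adverse event period cut. No new data are needed.

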Study Design: This is a multicenter, randomized, controlled, open-label extension study designed to assess the long-term safety and efficacy of AMG 145. Subjects that successfully complete a qualifying protocol and sign informed consent will be randomized 2:1 to one of two groups: AMG 145 + standard of care (SOC) or SOC-alone. Subjects randomized to the treatment group will also be expected to take background lipid lowering therapy and will be able to choose from one of two dose regimens: AMG 145 (140mg) administered every 2 weeks (Q2W) + SOC, or AMG 145 (420mg) administered monthly (QM) + SOC. Subjects randomized to the control group will receive SOC alone for the first 48 weeks of the study. During the first 12 weeks of the study participation, LDL-C will remain blinded and subjects must remain on stable background lipid lowering therapy. Using clinical judgment, the primary investigator or qualified delegate should recommend background lipid lowering therapy the subject can be expected to tolerate: therapy either prescribed to them PRIOR to participation in parent study, or statin or ezetimibe therapy given during parent study. Investigators will be informed if triglycerides are > 1000 mg/dL (11.3 mmol/L) so that appropriate subject follow-up can be initiated if necessary (see Protocol [Section 6.1.3.4](#)). Randomization should occur within 30 days after the parent study's EOS visit. Subjects will be stratified by their parent study and frequency of SC dose (Q2W or QM) within the parent study. After Week 48 all subjects will receive open-label AMG 145 for up to 2 years (or until the investigator's recommendation for discontinuation, Amgen's recommendation for discontinuation, the subject's decision to discontinue for any reason, or until an administrative decision is made to close the study).

Sample Size: The number of subjects entering this study will depend on the number of subjects completing their respective AMG 145 parent studies and willingness to enroll. Approximately 4428 subjects are expected to participate in this study.

Summary of Subject Eligibility Criteria: Subjects who complete a qualifying AMG 145 protocol and do not discontinue IP in the parent study for any reason including an adverse event will be eligible for this study. For a full list of eligibility criteria, please refer to [Section 4.1](#) and [Section 4.2](#).

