Amgen Investigational Product Dosage and Administration: AMG 145 will be administered via subcutaneous injection using a spring-based prefilled 1.0 mL auto-injector/pen (AI/Pen) or when available, a 3.5 mL Personal Injector.

AMG 145 will be administered via 1 of 2 regimens:

- AMG 145 140 mg SC Q2W (1 prefilled AI/Pen injection) or
- AMG 145 420 mg SC QM (3 prefilled AI/Pen injections or 1 Personal Injector, once made available)

The 3.5 mL Personal Injector will only be made available for use in this study once it has been determined that the intended user population for AMG 145 can safely and effectively use the device in clinical trials under guidance of study investigators.

Upon completion of the Week 12 Visit, subjects will have the opportunity to switch between Q2W and QM every 3 months, provided the appropriate supply of IP is available.

Non Amgen Investigational Product Dosage and Administration: None.

Control Group: The control group comprises of subjects randomized to SOC-alone during the first 48 weeks of study participation. Until laboratory results are unblinded at Week 12, the control group should remain on stable lipid lowering therapy (eg, therapy prescribed in parent study or the same therapy prescribed before parent study participation whichever the subject is likely to tolerate). After unblinding at Week 12, investigators may prescribe any concomitant medications or treatments deemed necessary to provide adequate supportive care (Section 6.3). After 48 weeks of participation, these subjects will receive open-label AMG 145 in the regimen of their choice (Q2W or QM) and will no longer be considered part of a control group. These subjects may also switch between regimens every 12 weeks.

Procedures: Prior to enrolling in this study, subjects will need to undergo end of study (EOS) procedures for their qualifying parent study. In addition, subjects will need to sign a new study Informed Consent Form and meet inclusion/exclusion criteria requirements. Subject identification numbers will be the same as those in their parent protocols.

Subjects that fall within a 30 day window of completing the final laboratory assessments for a qualifying parent study do not require laboratory procedures to be repeated.

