Subject visit schedule will differ based upon 3 factors: randomization, selection of Q2W or QM regimen, and prior experience with self-injection of AMG 145. Subjects randomized to AMG 145 + SOC without previous experience with self-injection of AMG 145 will have additional IP training visits at time of study start. At Week 48, a similar training schedule will be utilized for subjects randomized to SOC-alone at Day 1 with no previous experience with self-injection of AMG 145.

Additional visits will occur quarterly. During site visits vital signs, adverse events (AEs)/Serious Adverse Events (SAEs), and concomitant therapy will be evaluated. Other assessments and procedures include fasting lipids, physical exam, measuring body weight, laboratory assessments, including: anti-AMG 145 antibodies, urine pregnancy testing (females of childbearing potential), and urinalysis. IP administration by SC injection will be done after all other procedures have been completed.

Statistical Considerations

General Considerations

Statistical analyses in this multicenter, open label study will be descriptive.

There will be interim analyses to support safety data reporting and assessments of efficacy endpoints. In particular, interim analyses of the randomized study period (up to Week 48) will be conducted after all subjects from sets of parent studies have completed the Week 48 visit or ended the study.

For all endpoints, results will be summarized by the treatment group to which subjects are randomized in this study, unless otherwise specified.

Subject disposition, demographics and baseline characteristics will be summarized.

Summary statistics for continuous variables will include the number of subjects, mean, median, standard deviation or standard error, first and third quartiles, minimum, and maximum. For categorical variables, the frequency and percentage will be given. 95% confidence intervals will be calculated for select continuous and categorical endpoints.

Unless otherwise specified, the baseline value is defined as the subject's baseline value from the parent study.

The full analysis set (FAS) will include all subjects randomized in this study. All analyses of randomized controlled period of the study will be performed using the FAS. Analyses of the

period after the randomized controlled period may be limited to those receiving investigational product. There will be no imputation for missing data.

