10.1.2 Secondary Endpoints

- Percent change from baseline in LDL-C at Week 48 and Week 104
- Change from baseline in LDL-C at Week 48 and Week 104

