10.4.2.3 Exploratory Endpoint Analyses

The percent change and change from baseline in laboratory based exploratory endpoints at each scheduled visit will be summarized. For achieving LDL-C < 70 mg/dL, subjects missing LDL-C for a particular planned visit will be considered as not achieving LDL-C < 70 mg/dL. For continuous exploratory endpoints, the same model as for the secondary endpoint analyses may be used for estimating treatment group means and differences at weeks 48 and 104.

Subgroup analyses for exploratory endpoints may be conducted on baseline covariates specified in Section 10.1.6.

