10.4.2.4 Safety Endpoint Analyses

Safety Laboratory Parameters

Laboratory parameters will be summarized for each treatment group using descriptive statistics at each scheduled visit. Laboratory shift tables for certain analytes will be provided using the CTCAE v.4 toxicity criteria. The results will be based on the maximum (ie, worst) shift from baseline to the end of study.

Vital Signs

Vital signs will be summarized for each treatment group using descriptive statistics at each scheduled visit.

Anti-AMG 145 antibodies

The incidence and percentages of subjects who develop anti-AMG 145 antibodies (binding and neutralizing) at anytime will be tabulated.

Concomitant Medications

Concomitant medications of interest will be summarized for each treatment group.

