Appendix A. Schedule of Assessments

Applies to both AMG 145 and SOC-alone groups unless specified otherwise					
Timepoint/Frequency	W116	W128	W140	W152	EOS Phone visit W156
General Procedures					
Vital Signs (sitting BP, HR)	X	X	X	X	
Review for AEs/SAEs	X	X	X	X	X
Concomitant therapy	X	X	X	X	X
Physical Exam				X	
Body Weight				X	
Laboratory					
Fasting lipids				X	
Chemistry, fasting glucose				X	
Hematology				X	
Coagulation (PT/INR)				X	
HbA1c				X	
Anti-AMG 145 antibodies				X	
HCV viral load ^l				X	
Urine pregnancy				X	
Investigational Product					
IP Dispense	X	X	X		
IP Reconcile	X	X	X	X	

Page 3 of 3

^a D1 = day of first administration of IP. This visit should also coincide with EOS visit for parent study; for visit windows see [Section 7](#) of the protocol. Procedures NOT conducted as part of EOS visit for parent study should be completed at this visit.

^b Training visit applies to subjects who are randomized to AMG 145 and select the Q2W regimen

^c Training visit applies to subjects who are randomized to AMG 145 and select QM regimen

^d Only if enrollment into 138 exceeds last laboratory visit from parent study by 30 days. Cardiac History Form will also need to be completed.

^e Telephone visit for subjects randomized to SOC-alone

^f Only for subjects receiving AMG 145 who have selected the QM regimen

^g Only for subjects receiving AMG 145 who have selected the Q2W regimen

^h Vitamin E samples will be drawn for all applicable visits, testing will be conducted by reflex when LDL-C is < 25 mg/dL

ⁱ Training visit applies to subjects who are randomized SOC-alone in year 1 and select the Q2W regimen in year 2

^j Training visit applies to subjects who are randomized SOC-alone in year 1 and select the QM regimen in year 2

^k Only for subjects randomized to placebo or SOC in parent study AND randomized to SOC-alone in Year 1

^l HCV antibodies only in high risk subjects (see [Section 7.1.2.4](#)) or if ALT or AST > 2x ULN; viral load only in subjects positive for HCV

^m FSH in applicable subjects for study entry only – see [exclusion criteria](#); urine pregnancy in females of childbearing potential

ⁿ Dispense IP for at-home injections (only for subjects who have previous experience of self-injecting AMG 145)

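### The Week 104 group difference and the end-of-study worst lab shift use SOC-alone as comparator after it has switched to AMG 145

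*Protocol*

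**What the plan says.** Protocol 10.1.2 sets the secondary endpoints at two times, for example "Percent change from baseline in LDL-C at Week 48 and Week 104". Section 10.4.2.2 fits a mixed effects model with treatment by visit and then says "Differences in group means for the secondary and exploratory endpoints will be estimated between the AMG 145 + SOC group and the SOC-alone group". It sets no time limit. For continuous exploratory endpoints, 10.4.2.3 adds that the same model "may be used for estimating treatment group means and differences at weeks 48 and 104".

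The Synopsis describes the design differently. Under Study Design: "After Week 48 all subjects will receive open-label AMG 145 for up to 2 years". Under Control Group, the former SOC-alone subjects "will no longer be considered part of a control group". Under General Considerations: "For all endpoints, results will be summarized by the treatment group to which subjects are randomized in this study, unless otherwise specified".

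For laboratory shift tables, Protocol 10.4.2.4 says: "The results will be based on the maximum (ie, worst) shift from baseline to the end of study". There is no break at Week 48.

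The interim SAP (8.4.4) gives separate shift tables for a SOC-Controlled and an All-IP period. For a subject dosed at Week 48, SAP 5.1 ends the controlled period on the day before that dose and starts the All-IP period on the day of the dose. The Week 48 laboratory windows in SAP Appendix A open at the start of the All-IP period.

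**The concern.** The protocol asks for a contrast against a control group that, by its own account, no longer exists. At Week 48 the contrast is drug plus SOC against SOC alone, and that is sound. At Week 104 the same model, group names and label yield a different quantity: the effect of starting 48 weeks earlier when both groups are on drug. Nothing in 10.4.2.2 or 10.4.2.3 says so. Set beside the Week 48 difference, a small Week 104 figure could be read as loss of efficacy, and long-term LDL-C efficacy is the secondary objective.

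The laboratory table has a related problem. A worst shift to end of study, grouped as randomized, mixes off-drug and on-drug values in the SOC-alone column and pulls a relative safety signal toward no difference. The primary objective is safety. The SAP's period split is the natural remedy, but it places the Week 48 sample in the wrong period.

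**Working it through.** **The plan's own figures.** The documents give no figure for the Week 104 contrast or for shift rates. The one statistical figure, the precision statement in Protocol 10.2, reproduces. With 4428 subjects at 2:1 the groups are 1476 and 2952. Exact intervals for 74/1476 and 148/2952 are 3.96% to 6.25% and 4.25% to 5.86%, matching the stated 4.0% to 6.3% and 4.3% to 5.9%.

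**Exposure at Week 104.** AMG 145 + SOC: up to 104 weeks in this study. SOC-alone: 104 − 48 = up to 56 weeks.

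**Expected LDL-C difference at Week 104.** From uptake alone, difference = drug effect × gap between groups in the share on AMG 145. Assumed effect: 50 to 60 percentage points. Assumed gap: 0 to 0.20.
- Gap 0: 0 points, whatever the drug effect.
- Gap 0.20: 50 × 0.20 = 10 points; 60 × 0.20 = 12 points.

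The range is 0 to 12 points, or 0 to 20% of the drug effect.

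**Chemistry draws (Protocol Appendix A).** Post-baseline draws are at Weeks 12, 24, 48, 84, 104 and 152. For SOC-alone, Weeks 84, 104 and 152 are on drug: 3/6 = 50%. The Week 60 draw is "Only for subjects randomized to placebo or SOC in parent study AND randomized to SOC-alone in Year 1"; for those subjects it is 4/7 = 57%.

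**Worst shift, independent draws.** Assume a per-draw risk of 1% off drug and 2% on drug.

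| Window | AMG 145 + SOC | SOC-alone | Ratio | Difference (points) |
|---|---|---|---|---|
| Through Week 48 | 1 − 0.98³ = 5.88% | 1 − 0.99³ = 2.97% | 1.98 | 2.9 |
| To end of study | 1 − 0.98⁶ = 11.42% | 1 − 0.99³ × 0.98³ = 8.68% | 1.32 | 2.7 |
| To end of study, SOC-alone with Week 60 | 11.42% | 1 − 0.99³ × 0.98⁴ = 10.50% | 1.09 | 0.9 |

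**Worst shift, same subjects affected at every draw.** With 1% off drug and 2% on drug, the comparison is 2% v 1% through Week 48 (ratio 2.0, difference 1 point) and 2% v 2% to end of study (ratio 1.0, difference 0).

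**Worst shift, constant hazard.** Assume a 2% off-drug risk per 48 weeks and a hazard ratio of 2. Then risk = 1 − 0.98^((weeks off + 2 × weeks on)/48).
- Through Week 48: 3.96% v 2.00%, ratio 1.98, difference 1.96 points.
- To Week 152: exponents are 304/48 and 256/48, giving 12.01% v 10.21%, ratio 1.18, difference 1.80 points.
- Two-sided 5% power with 2952 and 1476 subjects falls from 0.95 to 0.42. This is illustrative only, as the study is descriptive.

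**The SAP split.** Protocol 6.1.1 and 7.1.1.14 require blood to be drawn before the dose at a site visit. A SOC-alone subject sampled and first dosed on the Week 48 visit day therefore has a sample with no in-study AMG 145 behind it. That day is the first of the All-IP period. The controlled-period table keeps 2 of the 3 off-drug draws (Weeks 12 and 24). On the current schedule the SOC-alone All-IP draws are Weeks 48, 84, 104 and 152, so 1 of 4 is pre-drug (1 of 5 with Week 60).

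**The case against.** The strongest reply is that this is a labelling matter in a descriptive study. No test, error rate or decision rests on Week 104. The Synopsis says openly that everyone receives AMG 145 after Week 48. A randomized early-versus-delayed contrast is a legitimate summary for an extension study, and the Week 104 difference in 10.4.2.3 is optional. Protocol 10.1.5 allows later analyses to be limited to those receiving drug, and 10.3 plans interim analyses confined to Week 48. Laboratory values are also summarized visit by visit, and the SAP already splits the shift tables.

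Much of this stands as a limit on severity. It does not remove the point:
- The difference in 10.4.2.2 is not optional and is not limited in time.
- Restricting to drug recipients puts both groups fully on drug, which moves the expected difference to about zero and does not restore a control.
- Section 10.3 concerns interim analyses. The SAP is an interim SAP that cites Amendment 2, while the protocol is at Amendment 6. No final SAP is among the documents.

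On the laboratory tables, the dilution is mainly in the ratio and in precision. The absolute difference barely moves under independent draws (2.9 to 2.7 points) or constant hazard (1.96 to 1.80). It vanishes only if the same subjects are affected at every on-drug draw. The grouping of the shift table by randomized arm is inferred from the Synopsis default, because the shift sentence does not name groups.

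The SAP window problem applies only to subjects dosed at Week 48. The period rule is not specific to one arm. Where it applies in both, the controlled table loses the same draw in each, which costs information and is not shown to cause bias.

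**Conclusion.** The concern holds and should be fixed, though it affects interpretation and not sample size or error rates. The Week 48 contrast is sound. The Week 104 contrast is early versus delayed start and is expected to be 0 to 12 points against an assumed drug effect of 50 to 60, with an assumed uptake gap of at most 20 points. In the protocol's end-of-study shift table, a true doubling of risk would show as a ratio of about 1.0 to 1.3, depending on the assumed pattern of events and on whether the Week 60 draw applies. The interim SAP's period split avoids most of this dilution. However, for subjects dosed at Week 48 it moves the last off-drug sample out of the controlled table and puts a pre-drug value into the SOC-alone All-IP table. Effect sizes, uptake and shift risks are all assumptions; the draw counts and exposure times come from the protocol.

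**What to change.** 1. **Protocol 10.4.2.2 and 10.4.2.3.** Limit the AMG 145 + SOC minus SOC-alone difference to visits through Week 48. At Week 104, report group means labelled *AMG 145 from Day 1* and *AMG 145 from Week 48*, and label any difference *early versus delayed start*. Optionally add the within-group change from Week 48 to Week 104.
2. **Protocol 10.4.2.4.** Adopt the SAP's period split: comparative worst-shift tables through the Week 48 pre-dose sample, and separate tables after it, each against parent-study baseline. Carry this into the final SAP.
3. **SAP 5.1 and Appendix A.** Assign the Week 48 pre-dose sample to the SOC-Controlled period, add a Week 48 row to that period's laboratory windows, and exclude the sample from the All-IP worst shift.

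The cost is protocol and SAP wording, one window rule and relabelled tables. No new data, visits or subjects are needed.
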